3.2 Summary Statistics

Data summaries are the same as described in the M-SAP.

3.3 Precision

Precision of reported results is the same as described in the M-SAP.

3.4 Transformations

Data transformations are the same as described in the M-SAP.

3.5 Multiplicity Adjustments

Handling of multiplicity adjustments is the same as described in the M-SAP.

3.6 Missing Data

Handling of missing data is the same as described in the M-SAP. Clinic-based assessments that are missing due to COVID-19 restrictions or disruptions are considered missing at random.

4. Study Endpoints

4.1 Efficacy Endpoints

The primary and secondary efficacy endpoints are the same as described in the M-SAP. ALSFRS-R total score is considered the primary efficacy endpoint and hand-held dynamometry (HHD) upper and lower extremity percentages, slow vital capacity (SVC), and survival are considered key secondary efficacy endpoints in RGA.

4.2 Exploratory Endpoints

The following categories of exploratory endpoints will be evaluated:

- Change in ALSFRS-R domain scores,
- Change in strength: HHD global percentage, HHD0, and HHD0²,
- Change in quantitative voice characteristics as measured by Aural Analytics: maximum phonation time, pause rate, breathy vocal quality, pitch instability, regulation of voicing, articulatory precision, speaking rate, articulation rate, and monotonicity,
- Change in biofluid biomarkers of neurodegeneration and neuromuscular degeneration: serum creatinine and serum and cerebrospinal fluid (CSF) neurofilament light chain (NfL),
- Change in patient-reported outcomes: ALSAQ-40 physical mobility, independence in activities of daily living, eating and drinking, communications, and emotional reactions domain scores and ALSAQ-40 symptom index, CNS-BFS total score,
- Change in respiratory function as assessed by home spirometry,
- Time to clinical events: first hospitalization due to a serious adverse event (SAE), first hospitalization due to an ALS-related SAE, first use of assisted ventilation, first placement of a feeding tube, first time reaching King's stage 4a or 4b, and first instance of any of the following events: hospitalization for an SAE, feeding tube placement, tracheostomy, initiation of permanent assisted ventilation (PAV), or death,
- Pharmacokinetics of zilucoplan and its two major metabolites (RA102758 and RA103488) in plasma and CSF, and
- Change in complement pathway biomarker levels in blood and CSF: sheep red blood cell (RBC) hemolysis assay and C5 levels.

4.3 Safety Endpoints

In addition to the safety endpoints described in the M-SAP, the following RGA regimen-specific safety endpoint will be evaluated:

- Immunogenicity against zilucoplan as assessed by incidence of anti-drug antibodies (ADA) and anti-PEG antibodies (anti-PEG-ADA).

5. Measurement Definitions

5.1 ALSFRS-R

The definitions of ALSFRS-R scores are the same as described in the M-SAP. Pre-baseline slope in ALSFRS-R (delta-FRS) is defined as 48 minus the baseline ALSFRS-R total score then divided by the number of months from onset of symptomatic weakness to the Baseline Visit. The number of months will be calculated as the difference in days from onset of symptomatic weakness to the Baseline Visit multiplied by 12 / 365.25. The date of onset of symptomatic weakness will be imputed as the fifteenth day of a month if not specified more precisely.

ALSFRS-R domain scores are exploratory measures of the primary efficacy endpoint ALSFRS-R total score.

5.2 SVC

The derivation of SVC percent-predicted of normal is the same as described in the M-SAP with age calculated as number of days from date of birth to the date of a given SVC assessment divided by 365.25 and with the following correspondence between self-identified race and race defined by Global Lung Initiative (GLI) classification:

Self-identified Race	GLI-defined Race
American Indian or Alaska Native	Mixed/Other
Asian	South East Asian
Black or African American	African American
Native Hawaiian or Other Pacific Islander	Mixed/Other
White	Caucasian
Unknown	Caucasian
Not reported	Caucasian
More than one race indicated	Mixed/Other

5.3 Home Spirometry

Home spirometry assesses FVC remotely using a smartphone app (ZEPHYRx, Albany, NY) and a handheld spirometer (Spirobank Smart, Medical International Research, Rome, Italy).

Coordinators guide participants through 3 to 8 maneuvers with live-video coaching using the ZEPHYRx platform. Flow loops are classified for acceptability and repeatability using American Thoracic Society (ATS) criteria and are manually reviewed by the NEALS Outcomes Center (Barrow Neurological Institute, Phoenix, AZ). The maximum FVC accepted by the NEALS Outcomes Center is converted to percent of predicted normal using GLI norms based on sex, age at time of assessment, height at time of screening, and race. Age is calculated as number of days from date of birth to the date of a given home spirometry assessment divided by 365.25. Higher values indicate greater respiratory function.

5.4 HHD and Grip Strength

The derivation of HHD upper and lower extremity scores and HHD0 are the same as described in the M-SAP with the revision that HHD0 is a composite endpoint with death or death equivalent, whichever occurs first.

A second HHD time-to-event endpoint is defined as the time from the Baseline Visit to the second post-baseline occurrence of a muscle with a strength recording of 0 among those muscles that were non-zero at baseline or time to death or death equivalent, whichever occurs first (HHD0²).

Time at risk for HHD0 and HHD0² will be censored at the last date at which an HHD assessment was performed up to the end of the Week 24 Visit window.

HHD global average percentage, HHD0, and HHD0² are exploratory measures of the secondary endpoint HHD and grip strength.

5.5 Quantitative Voice Characteristics

Voice samples will be collected using the Aural Analytics app installed on either an Android or iOS-based smartphone. At each assessment, participants perform a set of speaking tasks: reading

5 prespecified sentences, reading 5 sentences chosen at random from a large sentence bank, repeating a consonant-vowel sequence, producing a sustained phonation, and counting on a single breath. Speech analysis will be performed by Aural Analytics to derive the following quantitative voice characteristics: maximum phonation time, pause rate, breathy vocal quality, pitch instability, regulation of voicing, articulatory precision, speaking rate, articulation rate, and monotonicity. Aural Analytics will use quantitative voice characteristics data and participant age, sex, race, height, and weight to derive a prediction of vital capacity at the Baseline Visit.

5.6 Biofluid Biomarkers of Neurodegeneration

Blood biomarkers of neurodegeneration, including biomarkers of neuromuscular dysfunction, will be assayed. These will include serum creatinine and serum and CSF neurofilament light chain (NfL). Serum creatinine will be assayed by the kinetic Jaffe method (test 001370, Labcorp, Burlington, NC). NfL will be assayed by single-molecule array (Simoa; Quanterix, Billerica, MA). Levels of serum and CSF NfL that are reported to be below the limit of quantitation will be imputed at the limit of quantitation. Levels of serum and CSF NfL will be log-transformed in all analyses.

5.7 ALSAQ-40

The description of the ALSAQ-40 instrument and item-level scores are the same as described in the M-SAP. Each of the five domains will be scored as the mean of all domain-specific items multiplied by 25 (range 0 to 100). An overall symptom index (SI) will be scored as the mean of the five domain scores. A domain score will be missing if more than 20% of the items are missing; otherwise, item non-response will be mean-imputed from other completed items from the same assessment. The ALSAQ-40 SI will be missing if any domain scores are missing. Higher scores indicate worse quality of life.

5.8 CNS-BFS

The definition of CNS-BFS total score is the same as described in the M-SAP.

5.9 Survival

The primary definition of survival time is the same as described in the M-SAP with the clarification that PAV is defined as more than 22 hours per day of noninvasive or invasive mechanical ventilation for more than seven consecutive days. The date of PAV initiation, where applicable, will be imputed as the fifteenth day of a month if not specified more precisely. A secondary survival endpoint of death alone, independent of any death equivalent, is also defined.

Time at risk for the composite endpoint of death or death equivalent and time at risk for the endpoint of death alone will be measured from each participant's Baseline Visit. Time at risk will be censored at two time points: (1) at the Week 24 Visit as defined in the M-SAP, and (2) at a subsequent assessment of death or death equivalent scheduled approximately at the end of placebo-controlled follow-up of the last RGA participant. The primary analysis of survival will evaluate PAV-free survival to the Week 24 Visit time point.

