6.1.9 Week 24 Visit or Early Termination Visit

Participants should be instructed to hold study drug on the day of the study visit. Study drug should not be taken until after study visit procedures are complete.

The Week 24 Visit will take place in-person 168 ± 7 days after the Baseline Visit. The following procedures will be performed at either the Week 24 Visit or the Early Termination Visit:

- Home Spirometry
- ALSAQ-40
- CNS Bulbar Function Scale
- Voice Recording
- Uninstall Smartphone App
- Anti-drug Antibody Sampling
- Zilucoplan Plasma PK Analysis
- Zilucoplan Pharmacodynamic Analysis
- Zilucoplan Peripheral Blood Biomarker Samples
- Dispense investigational product to participant **[See note below.]**
- Remind participant to bring investigational product to the next visit (only if continuing in OLE)

Note: Drug is only dispensed at this visit if the participant is continuing in the Open Label Extension. Participants should be instructed to continue using effective contraception for at least 40 days after their last dose of study drug.

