5.10 King's ALS Clinical Staging System

The King's ALS Clinical Staging System (Roche et al. 2012) is a 4-level ordinal scale with the first three levels indicating the number (1, 2, or 3) of distinct central nervous system regions

(bulbar, upper limb, and lower limb) with neuromuscular dysfunction and levels 4a and 4b indicating nutritional or respiratory failure secondary to ALS, respectively.

Participants will be classified to King's stage 1, 2, 3, 4a, or 4b based on scores from ALSFRS-R assessments according to a published derivation (Balendra et al. 2014). Bulbar involvement is defined as a score less than 4 on any of the ALSFRS-R questions in the bulbar domain (questions 1, 2, and 3). Upper limb involvement is defined as a score less than 4 on either of the ALSFRS-R questions related to hand function (questions 4 and 5A). Lower limb involvement is defined as a score less than 4 on the ALSFRS-R question about walking (question 8). Nutritional failure is defined as responding that the participant uses gastrostomy for greater than 50% of their nutrition. Respiratory failure is defined as a score of 0 on the ALSFRS-R question addressing dyspnea (question 10 or R-1) or a score less than 4 on the ALSFRS-R question about use of mechanical ventilation (question 12 or R-3). Participants without evidence by ALSFRS-R scores of involvement of any of the three central nervous system regions will be scored as King's stage 1 due to their confirmed diagnosis with ALS. Participant may meet criteria for both King's stage 4a and 4b.

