6.3 Primary Efficacy Analysis and Supportive Analyses

The primary analysis for RGA is a Bayesian shared-parameter, repeated-measures model of ALSFRS-R that accounts for loss of follow-up due to mortality. Details of the model, including documentation of operating characteristics under a range of scenarios, are provided in the "ALS Master Protocol Recommended Statistical Analysis, Design and Simulation Report" (Appendix 1 to the Master Protocol). The Bayesian shared-parameter, repeated-measures model will be applied to the FAS analysis set as the primary analysis, to the ERO analysis set as a sensitivity analysis, and to the EPP analysis set as a supportive analysis.

The estimand of the primary analysis is the relative rate of disease progression (the "disease rate ratio" or DRR) of active treatment relative to placebo in the FAS population under an assumption that active treatment slows mean time to death or death equivalent by the same proportion as treatment slows the mean rate of functional progression as measured by change in ALSFRS-R total score over time. The estimand is defined by the following attributes:

- Treatment: zilucopan administered subcutaneously once daily at a dosage of approximately 0.3 mg/kg vs. placebo.
- Population: FAS population as defined in Section 6.1.
- Variables: time to death or death equivalent and rate of change in ALSFRS-R total score from baseline to the Week 24 Visit.
- Intercurrent event 1: treatment discontinuation due to death: no ALSFRS-R data from participants who reach the death or death equivalent endpoint are included in the analysis, handled via mortality component in model, composite variable strategy approach.
- Intercurrent event 2: treatment discontinuation not due to death: handled via treatment policy approach, all data will be used including data collected during the placebo-controlled period after treatment discontinuation regardless of concomitant medication, for those participants who have not been censored due to mortality. Missing data post-treatment will not be imputed, handled via missing at random assumption.
- Population-level summary: mean ratio of hazard or progression rate of active treatment relative to placebo.

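### SAP 5.9 dates every month-only start of permanent assisted ventilation to the 15th without checking recorded dates, so a few events can fall on the wrong side of Week 24

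*SAP*

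**What the plan says.** SAP 5.9 takes its survival definition from the Master SAP (M-SAP) and adds that "PAV is defined as more than 22 hours per day of noninvasive or invasive mechanical ventilation for more than seven consecutive days". For incomplete dates it gives one rule: "The date of PAV initiation, where applicable, will be imputed as the fifteenth day of a month if not specified more precisely". It does not mention the Baseline Visit, the last contact free of PAV, the first contact on PAV, or death as limits on the imputed date.

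The date matters for event status because "The primary analysis of survival will evaluate PAV-free survival to the Week 24 Visit time point", with time at risk censored "at the Week 24 Visit as defined in the M-SAP". Protocol 6.1.9 gives the timing: "The Week 24 Visit will take place in-person 168 ± 7 days after the Baseline Visit". Survival is fourth in the testing sequence (SAP 6.5.1) and is tested by log-rank in the Full Analysis Set, which includes shared placebo participants from regimens B, C and D (SAP 6.1). Death equivalent also enters the clinical-event composites (SAP 5.11), HHD0 and HHD0² (SAP 5.4) and CAFS (SAP 6.5.5). For the primary estimand, SAP 6.3 states that "no ALSFRS-R data from participants who reach the death or death equivalent endpoint are included in the analysis".

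The facts needed to bound the date are already collected. Vital status, including death equivalent, is determined for each randomized participant at the end of double-blind follow-up, generally at the Week 24 Visit (Protocol Schedule of Activities, note 17; SAP 2.9, note 21). SAP 6.5.4 lists the study day on which each participant was last known alive and free of a death equivalent.

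**The concern.** The rule is unconditional, so the imputed date can contradict the trial's own records. A participant documented free of PAV at Week 24 can be dated to an earlier event. A participant already on PAV at Week 24 can be dated to a later one and censored. A start can also be dated after death.

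Elsewhere the SAP is more careful. Incomplete adverse event onset dates have a rule for dates that span the start or end of the treatment-emergent interval (SAP 6.6.1). Time to King's stage 4a or 4b and to zero muscle strength is treated as interval censored between assessments (SAP 5.11 and 6.5.6). The PAV date, which decides events in a key secondary endpoint, has no such safeguard. What is at stake is whether some participants count as events by Week 24 and, for others, the time at which the event is placed.

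**Working it through.** The documents give no event count, PAV rate or share of month-only dates, so there is no plan figure to reproduce. The check is calendar arithmetic.

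**Worked dates** (illustrative, with Week 24 on day 168 and the start taken as the event date, since that is the date 5.9 imputes):

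| Baseline | Week 24 Visit | True start | Imputed date | Effect at the visit |
|---|---|---|---|---|
| 20 Apr 2021 | 5 Oct | 1-5 Oct (days 164-168) | 15 Oct (day 178) | Event moved out |
| 28 Apr 2021 | 13 Oct | 1-5 Oct (days 156-160) | 15 Oct (day 170) | Event moved out; eight days on PAV already completed by the visit |
| 5 Apr 2021 | 20 Sep | 21-30 Sep (days 169-178) | 15 Sep (day 163) | Later event moved in, although off PAV at the visit |

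The result does not depend on whether the M-SAP cuts off at the visit or at the end of its window (168 + 7 = day 175). In the first row, day 178 lies beyond the window. In the third row, starts on 28-30 Sep (days 176-178) are true post-window events that are dated inside it.

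**Week 24 Visit in the same month.** Assume that the true start day t and the visit day c are independent and uniform on a 30-day month (900 pairs), with a start on the visit day counting as an event.
- Moved out (t ≤ c and c ≤ 14): 1 + 2 + … + 14 = 105; 105/900 = 11.7%.
- Moved in (t > c and c ≥ 15): 15 + 14 + … + 0 = 120; 120/900 = 13.3%.
- Total: 225/900 = 25.0%.
- For 28 days: 105/784 + 91/784 = 13.4% + 11.6% = 25.0%. For 31 days: 105/961 + 136/961 = 10.9% + 14.2% = 25.1%.

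**Share of all month-only PAV events.** Assume a constant event rate over the 168 days and to the end of the month that contains Week 24.
- Moved out: 0.117 × 30/168 = 2.1%.
- Moved in: 0.133 × 30/168 = 2.4%.
- Total: 0.25 × 30/168 = 4.5%. Net: 2.4% - 2.1% = 0.3%.
- With an assumed 10 to 20 month-only PAV events, the expected number of crossings is 0.045 × 10 = 0.45 to 0.045 × 20 = 0.9.

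**Visit documented free of PAV in the same month, start after it.** There are 30 × 29/2 = 435 pairs, of which 120 have the visit on or after the 15th: 120/435 = 27.6% are dated on or before the visit (24.1% for 28 days, 29.2% for 31).

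**Death in the same month.** More than seven consecutive days is taken to mean a start at least 8 days before death. There are 1 + 2 + … + 22 = 253 pairs, of which 21 have death on or before the 14th: 21/253 = 8.3% are dated after death (10.0% for 28 days, 7.6% for 31). In those cases the composite event would occur at death, 8 to 13 days late. It remains an event.

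**The case against.** The strongest reply is that event status at Week 24 does not rest on the imputed date alone. Vital status is determined separately at that point, and SAP 6.5.4 lists each participant's status for each analysis timepoint. A careful programmer would probably notice a contradiction. That is fair, but no passage says that this determination overrides or bounds the imputed date, which is what fixes the event time.

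A second reply is that the M-SAP, which holds the base survival and censoring definitions, may contain a general consistency rule. SAP Section 1 gives this SAP precedence only where the two conflict, so such a rule could supplement 5.9. This cannot be checked here. As it stands, the 5.9 sentence is unqualified.

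A third reply is that mid-month imputation is this SAP's convention, also used for symptom onset (SAP 5.1). Symptom onset feeds a covariate measured in months or years. The PAV date decides whether an event counts.

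Two limits on the point stand in full. ALSFRS-R question 12 is not shown to record the 22-hour, seven-day definition; SAP 5.10 uses it only to mark mechanical ventilation. It therefore cannot date PAV, although a response of no mechanical ventilation does rule PAV out. The rule is also identical in both arms.

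**Conclusion.** The rule is wrong as written, but its effect is small. It can produce dates that contradict recorded PAV status or death. About 25% of month-only dates that share a month with the Week 24 Visit fall on the wrong side of it, or roughly 4-5% of all month-only PAV events, nearly offsetting in direction. These figures rest on uniform days within the month and a constant event rate. The number of month-only dates is unknown.

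Three stronger readings are tempting, and the documents do not support them:
- *A quarter of PAV events are misplaced.* The 25% applies only to month-only dates in the month of the boundary.
- *The survival comparison is biased, or loses a sizeable part of its information.* The rule is the same in both arms, the movements nearly cancel, and the test includes shared placebo participants as well as this regimen's own. A start dated after death only delays an event that still counts, and death alone is unaffected.
- *Misdated participants wrongly lose or keep ALSFRS-R data in the primary analysis.* The wording in SAP 6.3 invites this. However, the mortality model is specified in the design and simulation report (Appendix 1 to the Master Protocol), which SAP Section 1 ranks above this SAP for the primary analysis. Whether it uses the 5.9 date could not be checked.

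**What to change.** Replace the sentence in SAP 5.9 with wording such as:

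> If only the month of PAV initiation is known, the date is set to the fifteenth when that day lies in the feasible interval, and otherwise to the midpoint of the interval, rounded down. The interval runs from the latest of the first day of the month, the Baseline Visit and the day after the last date documented free of PAV, to the earliest of the last day of the month, the first date documented on PAV and the date of death.

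Take the bounds from the PAV, event and vital-status records. Use ALSFRS-R question 12 only where it shows no mechanical ventilation. Query the site if the bounds conflict, and apply the rule blind to treatment.

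Contradictions with the recorded bounds then fall to zero by construction, as does misplacement across the Week 24 Visit where PAV status is recorded there. An imputed start may still lie fewer than eight days before a death in the same month, but the participant counts as an event either way. The cost is this change of wording and slightly more derivation code, with no new data.

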5.10 King's ALS Clinical Staging System

The King's ALS Clinical Staging System (Roche et al. 2012) is a 4-level ordinal scale with the first three levels indicating the number (1, 2, or 3) of distinct central nervous system regions

(bulbar, upper limb, and lower limb) with neuromuscular dysfunction and levels 4a and 4b indicating nutritional or respiratory failure secondary to ALS, respectively.

Participants will be classified to King's stage 1, 2, 3, 4a, or 4b based on scores from ALSFRS-R assessments according to a published derivation (Balendra et al. 2014). Bulbar involvement is defined as a score less than 4 on any of the ALSFRS-R questions in the bulbar domain (questions 1, 2, and 3). Upper limb involvement is defined as a score less than 4 on either of the ALSFRS-R questions related to hand function (questions 4 and 5A). Lower limb involvement is defined as a score less than 4 on the ALSFRS-R question about walking (question 8). Nutritional failure is defined as responding that the participant uses gastrostomy for greater than 50% of their nutrition. Respiratory failure is defined as a score of 0 on the ALSFRS-R question addressing dyspnea (question 10 or R-1) or a score less than 4 on the ALSFRS-R question about use of mechanical ventilation (question 12 or R-3). Participants without evidence by ALSFRS-R scores of involvement of any of the three central nervous system regions will be scored as King's stage 1 due to their confirmed diagnosis with ALS. Participant may meet criteria for both King's stage 4a and 4b.

